1.1 Synopsis

| Title: | A Pandamized Non Inferiority Study of a Hydrogal Deaking System |
|-------------------------|--|
| Title: | A Randomized, Non-Inferiority Study of a Hydrogel Packing System Compared to Standard of Care Packing During Image-Guided High-Dose Rate Brachytherapy Boost for Cervical Cancer |
| Study Description: | Brachytherapy is administered in conjunction with external beam radiation therapy and concurrent chemotherapy in women with locally advanced cervical cancer and is an essential component of curative therapy for this disease. Contemporary high-dose rate (HDR) brachytherapy is commonly delivered in 4-6 separate fractions on an outpatient basis with conscious sedation or mild oral sedation. |
| | Vaginal packing is a mandatory component of cervical cancer brachytherapy,¹ serving to displace the rectum and bladder from the high-dose regions and to stabilize brachytherapy applicators (Figure 2). Traditional vaginal packing methods include vaginal gauze packing (VGP) and rectal retractors (also called posterior vaginal speculum blades or rectal blades). VGP has been the preferred packing method in most centers due to its availability and low cost, but it causes patient discomfort and lacks reproducibility since it is highly dependent upon physician placement.² Rectal retractors provide some displacement of the rectum but do not displace the bladder. Additionally, they are difficult to place due to device crowding from the vertical column of applicators and rectal retractor. Vaginal balloon packing (VBP) methods have been developed to provide a more comfortable and reproducible method of vaginal packing, but these are expensive.²-¹ The high cost limits uptake of VBP in the US, since hospitals must absorb this cost for a treatment that already delivers relatively poor reimbursement compared to other radiation modalities.³ Current packing options are suboptimal for contemporary image-guided brachytherapy delivered on an outpatient basis under mild sedation. |

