8 STUDY ASSESSMENTS AND PROCEDURES

8.1 Clinical Assessments

8.1.1 Physical Exam

A complete physical exam will be completed at screening. Karnofsky performance status (KPS) or ECOG status will be collected at the time of each physical exam.

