9.1.5 Time Period and Frequency for Event Assessment and Follow-Up

The occurrence of an adverse event (AE) or serious adverse event (SAE) may come to the attention of study personnel during study visits and interviews of a study participant presenting for medical care, or upon review by a study monitor.

All AEs including local and systemic reactions not meeting the criteria for SAEs will be captured on the appropriate case report form (CRF). Information to be collected includes event description, time of onset, clinician's assessment of severity, relationship to study product (assessed only by those with the training and authority to make a diagnosis), and time of resolution/stabilization of the event. All AEs occurring while on study must be documented appropriately regardless of relationship. All AEs will be followed to adequate resolution.

Any medical condition that is present at the time that the participant is screened will be considered as baseline and not reported as an AE. However, if the study participant's condition deteriorates at any time during the study, it will be recorded as an AE.

Changes in the severity of an AE will be documented to allow an assessment of the duration of the event at each level of severity to be performed. AEs characterized as intermittent require documentation of onset and duration of each episode.

Version Date: 11/16/2021

Study staff will record all reportable events with start dates occurring any time after brachytherapy fraction 2 is completed until 30 days (for non-serious AEs) or anytime (for SAEs considered related to the study intervention) after the last day of study treatment. At each study visit, the investigator will inquire about the occurrence of AE/SAEs since the last visit. Events will be followed for outcome information until resolution or stabilization.

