10 STATISTICAL CONSIDERATIONS

10.1 Design

This is a two-center, stratified and randomized, four period, two arm crossover, noninferiority trial to demonstrate that BrachyGel Vaginal Hydrogel Packing System (hydrogel) is non-inferior to standard method vaginal packing (standard) in dose thresholds for D2cc (in Gy) for rectum and bladder by more than a non-inferiority margin of δ =1 Gy. Outcomes will be measured after each of 5 treatment fractions with results from the 1st fraction serving as the baseline measurement for each participant. D2cc measurements within organs varies between fractions as well as by participants, thus, each participant will receive both types of vaginal packing with order of packing type being chosen at random. Specifically, all participants will receive the standard method during the 1st fraction and then either sequence A (standard-hydrogel-standard-hydrogel) or sequence B (hydrogelstandard-hydrogel-standard) chosen at random, for the remaining four fractions. It is possible for participants to require less therapy during the final fraction (ie maximum therapy has been applied to the tumor), thus, the choice of ordering is limited to these two orderings to ensure that both packing types are administered to each participant with the primary assessment based upon fraction 2 and 3 data (ie, a two period, two treatment crossover).

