13 APPENDICES

13.1 Schedule of Activities (SoA)

| Procedures | Screening (within 6 weeks of Brachytherapy 1) | Brachytherapy 1 | Brachytherapy 2 | Brachytherapy 3 | Brachytherapy 4 | Brachytherapy 5 | 30 Day +/- 2 weeks Safety Follow-up |
|---|---|-----------------|-----------------------|-----------------|-----------------|-----------------|---|
| Informed consent | Х | | | | | | |
| Demographics | Х | | | | | | |
| Baseline conditions/assessment | X ² | | | | | | |
| Randomization | | | X ⁵ | | | | |
| Brachytherapy ¹ | | X^4 | Χ | Χ | Χ | Χ | |
| Physical exam | X ² | | | | | | X |
| Performance status | X ² | | | | | | X |
| Concomitant medications related to pain control during procedure ⁷ | | | Х | Х | Х | Х | |
| Physician Assessments of imaging/packing experience | | | Х | Х | Х | Х | |
| Physicist Assessments of imaging/packing experience | | X ⁶ | Х | Х | Х | Х | |
| Participant survey ³ | | | Х | Х | Х | Х | |
| Adverse event review and evaluation | | | X | | | X | Х |

Version Date: 11/16/2021

¹ Alternations will be based on Arm Assignment according to *Figure 1*.

² Must occur within 30 days of Brachytherapy 1. The assessments can be collected on the same day as Brachytherapy 1.

³ Participant survey should be completed without 1 hour following removal of packing after completion of brachytherapy. Not collected if participant was sedated.

⁴ Brachytherapy 1 is considered to be a part of the screening visit. Brachytherapy 2 is considered to be the "start of treatment." Brachytherapy 1 must occur within 14 days of registration.

⁵ No sooner than 10 days before Brachytherapy 2.

⁶ Only the dosimetry measurements need to be collected for Brachytherapy 1.

⁷ Not collected if participant was sedated.

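### The toxicity baseline is taken once, up to 30 days before fraction 1, and section 9.1.5 gives conflicting rules on when adverse-event recording starts

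*Combined protocol and SAP*

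**What the plan says.** **Timing of the baseline.** In the Schedule of Activities (13.1), the row "Baseline conditions/assessment" is marked in the Screening column only. Footnote 2 says "Must occur within 30 days of Brachytherapy 1" and adds "The assessments can be collected on the same day as Brachytherapy 1". Section 8.1.1 states "A complete physical exam will be completed at screening"; the schedule's only other examination is at the 30-day follow-up. Footnote 4 says "Brachytherapy 1 is considered to be a part of the screening visit" and treats fraction 2 as the start of treatment. Adverse-event review is not marked at fraction 1; it is first marked at fraction 2.

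**What the baseline is for.** Section 9.1.5 says "Any medical condition that is present at the time that the participant is screened will be considered as baseline and not reported as an AE".

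**When recording starts.** The same section has staff record reportable events whose start date falls after fraction 2 has been completed. It also says that a condition that worsens at any point in the study is recorded, that every on-study adverse event is documented whatever its relationship, and that each visit asks about events since the previous one. Section 9.1.1 confines adverse events to those at least possibly related to the study intervention.

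**Contrast with dosimetry.** For the dose measurements, section 10.1 has "results from the 1st fraction serving as the baseline measurement for each participant".

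**The concern.** The Synopsis says "Brachytherapy is administered in conjunction with external beam radiation therapy and concurrent chemotherapy in women with locally advanced cervical cancer". New pelvic toxicity between an early baseline form and the first randomised packing is therefore plausible from treatment that has nothing to do with packing. Diarrhoea, cystitis and proctitis are among the expected events in Table 2, and vaginal pain and inflammation are among the acute vaginal adverse events (aVAE) in section 10.5.

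The secondary safety objective concerns frequency, intensity and duration of events, and section 10.6 summarises them by packing type for fractions 2-5. Judging whether a finding is new or worse, and how long it has lasted, needs a grade from just before the packing. Without one, a toxicity already present at fraction 2 may be left out, or counted as new and linked to the packing used there: standard in Arm A, BrachyGel in Arm B. The study is unblinded (6.4) and BrachyGel has not been used in living patients (2.2.5), so relatedness judgements would gain from a documented pre-packing state.

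**Working it through.** The plan states no figure on this point. The check is date arithmetic followed by a comparison of the recording rules.

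**Age of the baseline at the first randomised packing**

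Inputs:
- a = days from baseline form to fraction 1: 0 to 30 (13.1, footnote 2).
- b = days from fraction 1 to fraction 2: about 2 to 7 (Synopsis, participant duration).
- Delays follow institutional guidelines, with no protocol maximum (6.2.1).

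Formula: age = a + b.
- Form on the day of fraction 1: 0 + 2 = 2 to 0 + 7 = 7 days.
- Form 30 days before fraction 1: 30 + 2 = 32 to 30 + 7 = 37 days.
- Any delay of fraction 1 or fraction 2 after the form adds to these.
- If footnote 4 is read to make conditions present at fraction 1 part of baseline, the uncovered interval is 2 to 7 days in every case. No baseline form is scheduled at fraction 1 to document those conditions.

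**How a toxicity is handled, by onset**

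| Onset | Start-date sentence in 9.1.5 | Other sentences in 9.1.5 |
|---|---|---|
| After the form, before fraction 1 | Not recorded; baseline only if footnote 4 extends screening, and then with no form | Recorded, or recorded if it worsens |
| Between fractions 1 and 2 | Not recorded, and not baseline | Recorded through the look-back question at fraction 2, although 9.1.1 requires a link to an intervention that has not begun |
| During the fraction 2 packing | Not recorded, because fraction 2 is not complete | Recorded |
| After fraction 2 | Recorded | Recorded |

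The rules agree only in the last row. In the first two rows, even where the event is recorded, no scheduled form holds its grade just before packing. The third row concerns a trial packing itself: each participant has four randomised packings (fractions 2-5), and read literally the window opens after the first of the four.

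**Direction of any bias**

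Suppose a proportion c of participants bring an existing toxicity to fraction 2 and it is credited to the packing used there. Under equal allocation, half fall on each packing: the standard rate becomes p_S + c/2 and the BrachyGel rate p_G + c/2. The difference, p_G - p_S, is unchanged in expectation. A ratio is diluted and the noise rises.

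**The case against.** The strongest reply is that the plan already has several nets. Section 9.1.5 calls for recording deterioration and all on-study events and asks about the time since the last visit. Section 8.1.2 has a clinician evaluate each participant at every visit with CTCAE version 5. The schedule marks adverse-event review at fraction 2. Footnote 4 arguably brings fraction 1 into screening. This stands in part: a reader might infer that toxicity arising in the gap belongs neither to the baseline nor to the recorded events, and the documents do not support that as the only reading. But these sentences contradict the start-date sentence, so two sites could treat the same event differently in good faith, and none of them schedules a pre-packing grade.

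Second, a 37-day-old baseline is the worst case, since same-day collection is allowed. That stands. A 30-day window chosen to match standard practice is a legitimate design choice in itself.

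Third, misattribution is not automatic. Section 9.1.3.2 has relationship to brachytherapy and to the packing system assessed separately. An event in the stopping count must be at least possibly related to BrachyGel and fall within 30 days of its first use. This stands as a limit on the effect, but a clinician judging relatedness would still do better with a recorded prior grade.

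Fourth, a reader might infer a bias towards no difference. With randomised order that is not shown for an absolute difference, as the calculation above indicates.

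**Conclusion.** The point holds as a potentially stale toxicity baseline combined with an unreconciled start for adverse-event recording. At the first randomised packing the baseline is about 2-7 days old at best and about 32-37 days at worst, assuming the stated fraction spacing and no delay. The consequence is noise and possible misattribution in a descriptive secondary comparison, and less secure relatedness judgements for the aVAE count. An effect on that count is possible but not quantified. The primary D2cc endpoint, sample size and power are not affected.

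The number of participants affected cannot be derived. A reader might assume that 10-30% of the 57 planned participants develop new toxicity in the gap (0.10 x 57 = 5.7 and 0.30 x 57 = 17.1, so about 6-17). That percentage is only an assumption. The rates in section 2.3.1, such as up to 24.5% for urinary morbidity and 28-33% for lower-grade bowel symptoms, come from cohorts who received brachytherapy and are not incidence between screening and fraction 2. Nor do the documents say when external beam treatment falls relative to the baseline form.

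**What to change.** 1. In the Schedule of Activities, add a baseline entry at Brachytherapy 2, completed before packing is placed, with CTCAE grades for the terms in Table 2 and section 10.5.
2. In 9.1.5, name that entry as the reference for all on-study adverse events, in place of conditions present at screening.
3. Keep the 30-day window for the physical examination and performance status.
4. Reconcile 9.1.1, 9.1.5 and 13.1 to a single start of adverse-event recording that includes events during the fraction 2 packing. The new form alone would not do this: the current start-date sentence would still exclude those events.

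Possible text for 9.1.5: *CTCAE grades recorded at Brachytherapy 2 before packing placement are the baseline. Any event that begins or worsens from the start of that placement onward, including during the packing, is recorded as an adverse event if it meets the definition in 9.1.1.* The sentence on documenting events regardless of relationship would need to be aligned with 9.1.1 at the same time.

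Cost: a few minutes of extra data entry per participant. A clinician evaluation and an adverse-event review already take place at fraction 2, so no visit or procedure is added.

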13.2 Physicist/Dosimetrist Case Report Form

| Pri | nt Name | Signature Date | |
|-----|--|---|----|
| | | | _ |
| | No distinction between | n packing and OARs (organs at risk) | |
| | 9 | een packing and OARs (organs at risk) | |
| | _ | een packing and OARs (organs at risk) | |
| | • | between packing and OARs (organs at risk) | |
| | ○ N/A (1st Brachytherap | , | |
| 2. | | the packing (i.e. ability to discern packing from pelver most appropriate response below: | ic |
| | O Poor filling of space | | |
| | Fair filling of space | | |
| | Good filling of space | | |
| | Excellent filling of spa | ce | |
| | ○ N/A (1st Brachytherap | y Fraction) | |
| 1. | Please rate the completeness appropriate response below: | of the packing by clearly selecting the mo | st |
| | D2cc: Gy | D2cc: Gy | |
| | D1 cc: Gy | D1 cc: Gy | |
| Bla | dder: D0.1 cc: Gy | Rectum: D0.1 cc: Gy | |
| HR | -CTV D90: Gy | | |
| | | | |
| Pre | escription dose: Gy | | |
| Αp | plicator: | | |
| Pa | cking Method: | | |
| Fra | action: of 5 | | |
| Sul | bject ID: | | |
| Da | te: | | |

13.3 Participant Packing Discomfort Assessment / Evaluación de la Incomodidad

del Empague de la Participante Date/Fecha: Subject ID/ ID del Sujeto: Fraction/ Fracción: _____ of 5 Packing Method/ Método de Empaque: _____ Applicator/ Aplicador: Please rate your discomfort during the entire brachytherapy treatment. / Califique 1. su malestar durante todo el tratamiento de braquiterapia No discomfort/ Sin molestias Mild discomfort/ Molestias leves Moderate discomfort/ Molestias moderadas Severe discomfort/ Molestias severas 2. Please rate your discomfort during the vaginal packing placement and removal. / Califique su molestia durante la colocación y extracción del empaque vaginal. No discomfort/ Sin molestias Mild discomfort/ Molestias leves Moderate discomfort/ Molestias moderadas Severe discomfort/ Molestias severas Questionnaire Completed by/ Cuestionario completado por: Participant/ Participante Administrator/ Administrador

CONFIDENTIAL 43

Signature/ Firma

Date/Fecha

Print Name/ Escriba su Nombre

13.4 Physician Case Report Form Date: Subject ID: Fraction: of 5 Packing Method: Applicator: ____ 1. Please rate the completeness of the packing by clearly selecting the most appropriate response below: Excellent filling of space Good filling of space Fair filling of space Poor filling of space 2. Please rate the imaging clarity of the packing (i.e. ability to discern packing from pelvic organs) by clearly selecting the most appropriate response below: O Very clear distinction between packing and OARs (organs at risk) Clear distinction between packing and OARs (organs at risk) Poor distinction between packing and OARs (organs at risk) No distinction between packing and OARs (organs at risk) 3. Please rate the ease of packing placement and removal by clearly selecting the most appropriate response below: Extremely easy Somewhat easy Somewhat difficult Extremely difficult Unable to rate Print Name Signature Date

13.5 Protocol Amendment History

Version Date: from 3/31/2021 to 11/16/2021

| Version Date: from 3/31/2021 to | |
|--|---|
| Section(s) | Description of Change |
| Title Page, Key Roles and Study Governance, ABBREVIATIONS, 1.1 Synopsis, 4.1 Overall Study Design, 10.2 Randomization and Stratification, | Updated site contact information and changed UPMC to AHN. |
| 11.1.4 Safety Oversight | |
| Rationale: UPMC has not/will no site has been changed to AHN. | t be participating as an additional site for the trial. The additional |
| 8.2 Participant reported outcomes | Reworded to include the options for completing the participant surveys. Participants can either complete a paper survey of the questions or a team member can read the questions/answers and record the participant's selections. |
| independently. | no impact in having participants answer the questions on paper |
| 9.1.1 Definition of Adverse Events (AE) | Redefined AEs to be any untoward medical occurrence associated (at least possibly related) with the use of the study intervention(s) |
| definition captures pertinent stand | reamlines the capture of AEs without underreporting. This dard clinical care and intervention related AEs of any category. |
| 9.1.7 Serious Adverse Event Reporting, 9.2.2 Reporting of UADE, 9.5.2 Unanticipated Problem Reporting, 9.6.2 Reporting a Data Breach, 9.7.3 Reporting of a Protocol Deviation or Exception | Restructured the reporting guidelines to specify which entities perform which requirements based on site type. |
| Rationale: For clarity on which re which are performed by the UVA | |
| 10.4 Sample Size and Accrual | Changed the total maximum enrollment goal from 70 to 57 |
| Rationale: To better align with th | e study budget. |
| 13.1 Schedule of Activities (SoA) | Updated calendar footnotes and increased timeframe for the collection of baseline physical exam, performance evaluation and conditions from within 3 days of Brachytherapy 1 to 30days. |
| Rationale: For clarity and to alig | n with SOC practice. |
| 13.2 Physicist/Dosimetrist Case Report Form, 13.3 Participant Packing Discomfort Assessment, 13.4 Physician Case Report Form | Updated formatting of Questionnaires and added Spanish translation to the participant discomfort survey. |
| Rationale: For functionality and survey questions on paper independent | to allow Spanish speaking participants the option to complete the endently. |

Version Date: from 6/25/2020 to 3/31/2021

| Section(s) | Description of Change |
|----------------------|---|
| 1.2 Schema | Removed "after 1st fraction of brachytherapy" from the |
| 5.8 Registration and | randomization time limit. The randomization timeframe is "10 days |
| Randomization | prior to 2 nd fraction" |

| 9.2 Randomization and | |
|--|--|
| stratification | |
| | there is no statistical reason to limit randomization to after the |
| first brachytherapy. | |
| 5.1 Inclusion Criteria | Updated Inclusion criteria 2 and exclusion criteria 1 & 3 to clarify |
| 5.2 Exclusion Criteria | that radiation therapy that is a part of the patient's current definitive |
| | treatment plan for the cancer of interest is acceptable |
| Rationale: It is common for the | he study's patient population to receive a combination of EBRT, |
| | rapy as definitive treatment. The intent is to not exclude individuals |
| | are a part of their current treatment plan for cervical cancer. |
| Abbreviations | Changed KPS to KPS or ECOG |
| 5.1 Inclusion Criteria | |
| 8.1.1 Physical Exam | |
| Rationale: For flexibility base | ed on standard practice |
| E E Description of Study | Added a description of the Arm assignments and details about |
| 5.5 Description of Study | Added a description of the Arm assignments and details about |
| intervention | fraction 1. In the section 1. In all the section with s |
| 4.1 | orial clarity of the assignments and to aligh this section with section |
| 6.3 Product Storage and | Added "after manufacture" |
| Stability | |
| Rationale: For additional clar | rity on the expiration of the device. |
| 5.8 Registration and | Added statement "eligibility and registration can occur after 1st |
| Randomization | fraction but before 2 nd fraction" |
| | s considered a "screening procedure" and the second is considered |
| | ty confirmation and registration do not need to occur before the first |
| fraction. | ty committation and registration do not need to occur before the mist |
| 7.2 Participant reported | Added "both standard and BrachyGel" |
| outcomes | Reworded "period" to "fraction 2-5" |
| 7.3 Physicist and Physician | Added statement about only dosimetry measurements data will be |
| reported outcomes | collected from Fraction 1 |
| 9.3.2 Study Outcomes & | Added statement that sedated patients will not be asked the patient |
| Endpoints | survey questions |
| | or/physicist surveys only need to be completed starting at fraction 2 |
| | the start of treatment. Fraction 1 is considered a part of "screening" |
| | ollected will be used as baseline values per section 9.1. Since the |
| | s are exploratory, sedated patients can still be enrolled as data for the |
| | and expresenterly, deducted parties the carrie and are detailed to the |
| primary endpoints can still be | collected. |
| primary endpoints can still be 8.1.4 Abnormal Laboratory | |
| 8.1.4 Abnormal Laboratory | Reworded to state that Abnormal laboratory values will not be |
| 8.1.4 Abnormal Laboratory Values | |
| 8.1.4 Abnormal Laboratory Values 8.1.5 Time Period & | Reworded to state that Abnormal laboratory values will not be |
| 8.1.4 Abnormal Laboratory Values 8.1.5 Time Period & Frequency for Event | Reworded to state that Abnormal laboratory values will not be |
| 8.1.4 Abnormal Laboratory Values 8.1.5 Time Period & Frequency for Event Assessment & Follow up | Reworded to state that Abnormal laboratory values will not be considered AEs and will not be recorded or reported |
| 8.1.4 Abnormal Laboratory Values 8.1.5 Time Period & Frequency for Event Assessment & Follow up Rationale: Lab values are no | Reworded to state that Abnormal laboratory values will not be considered AEs and will not be recorded or reported of being collected or assessed for the study. Lab values are typically |
| 8.1.4 Abnormal Laboratory Values 8.1.5 Time Period & Frequency for Event Assessment & Follow up | Reworded to state that Abnormal laboratory values will not be considered AEs and will not be recorded or reported of being collected or assessed for the study. Lab values are typically by as SOC. |
| 8.1.4 Abnormal Laboratory Values 8.1.5 Time Period & Frequency for Event Assessment & Follow up Rationale: Lab values are no not collected for brachythera | Reworded to state that Abnormal laboratory values will not be considered AEs and will not be recorded or reported of being collected or assessed for the study. Lab values are typically by as SOC. |
| 8.1.4 Abnormal Laboratory Values 8.1.5 Time Period & Frequency for Event Assessment & Follow up Rationale: Lab values are no not collected for brachytheray 10.1.2 Consent Procedures and Documentation | Reworded to state that Abnormal laboratory values will not be considered AEs and will not be recorded or reported of being collected or assessed for the study. Lab values are typically by as SOC. Added verbal consenting information for doctors and physicists |
| 8.1.4 Abnormal Laboratory Values 8.1.5 Time Period & Frequency for Event Assessment & Follow up Rationale: Lab values are no not collected for brachytherap 10.1.2 Consent Procedures and Documentation Rationale: Doctors and physical | Reworded to state that Abnormal laboratory values will not be considered AEs and will not be recorded or reported of being collected or assessed for the study. Lab values are typically by as SOC. Added verbal consenting information for doctors and physicists |
| 8.1.4 Abnormal Laboratory Values 8.1.5 Time Period & Frequency for Event Assessment & Follow up Rationale: Lab values are no not collected for brachytherap 10.1.2 Consent Procedures and Documentation Rationale: Doctors and physical | Reworded to state that Abnormal laboratory values will not be considered AEs and will not be recorded or reported of being collected or assessed for the study. Lab values are typically by as SOC. Added verbal consenting information for doctors and physicists sicists who plan to complete the Physician and Physicist Assessment cipants. Verbal informed consent needs to be obtained |
| 8.1.4 Abnormal Laboratory Values 8.1.5 Time Period & Frequency for Event Assessment & Follow up Rationale: Lab values are no not collected for brachytherap 10.1.2 Consent Procedures and Documentation Rationale: Doctors and phys Surveys are considered partic | Reworded to state that Abnormal laboratory values will not be considered AEs and will not be recorded or reported ot being collected or assessed for the study. Lab values are typically by as SOC. Added verbal consenting information for doctors and physicists sicists who plan to complete the Physician and Physicist Assessment |
| 8.1.4 Abnormal Laboratory Values 8.1.5 Time Period & Frequency for Event Assessment & Follow up Rationale: Lab values are no not collected for brachytheray 10.1.2 Consent Procedures and Documentation Rationale: Doctors and phys Surveys are considered partic 11.2.1 Data Collection and | Reworded to state that Abnormal laboratory values will not be considered AEs and will not be recorded or reported of being collected or assessed for the study. Lab values are typically by as SOC. Added verbal consenting information for doctors and physicists sicists who plan to complete the Physician and Physicist Assessment cipants. Verbal informed consent needs to be obtained |

Version Date: 11/16/2021

Version Date: 25 June 2020

multisite study.

| - 0 | | |
|-----|------------|-----------------------|
| | Cootion(o) | Description of Change |
| | Section(s) | Description of Change |
| | 000(0) | |

| Key Roles and Study | [name] was shifted from Medical Monitor to Sub-Investigator | |
|---|---|--|
| Governance | | |
| Rationale: [name] nee | eds to be able to participate as a sub-investigator in order to perform | |
| brachytherapy and cannot se | rve as both the medical monitor AND a co-investigator. | |
| 1.1 Synopsis | Expanded the range of stages to include IB1 and IVB | |
| 5.1 Inclusion Criteria | | |
| Rationale: While uncommon | , patients with these stages of disease may receive brachytherapy as | |
| definitive treatment for cervical cancer and there is no reason to exclude them from participation | | |
| 6.5 Concomitant Therapy | Changed "during the procedure" to "for the procedure" | |
| . , | | |
| Rationale: In some cases pain medication for the procedure may be given prior to the procedure | | |
| or just following, and this should also be captured. | | |
| 13.1 Schedule of Activities | "Medical History" was updated to "Baseline conditions/assessment" | |
| (SOA) | | |
| Rationale: A true history is not necessary, but an assessment of baseline conditions is required in | | |
| order to assess adverse ever | nts | |
